2.1.1.5 On-treatment assessment/event and observation periods

For all safety reporting the overall observation period will be divided into three mutually exclusive segments:

- **pre-treatment period:** from day of subject's informed consent to the day before first administration of study treatment
- **on-treatment period:** from date of first administration of study treatment to 30 days after date of last administration of study treatment (including start and stop dates)
- **post-treatment period:** starting at Day 31 after last administration of study treatment.

If dates are incomplete in a way that clear assignment to pre-, on-, post-treatment period cannot be made, then the respective data will be assigned to the on-treatment period.

Safety summaries (tables, figures) include only data from the on-treatment period with the exception of baseline data which will also be summarized where appropriate (e.g., change from baseline summaries). In addition, a separate summary for death including on-treatment and post-treatment deaths will be provided. In particular, summary tables for AEs will summarize only on-treatment events, with a start date during the on-treatment period (treatment-emergent AEs).

2.1.1.6 Last contact date

The last contact date will be derived for subjects not known to have died at the analysis cut-off using the last complete date among the following data sources ([Table 2-1](#)).

Table 2-1 Last contact date data sources

Source data	Conditions
Last contact date/last date subject was known to be alive from Survival eCRF page	Patient status is reported to be alive or unknown in the survival eCRF page
Start/End dates from further antineoplastic therapy	Non-missing medication/procedure term
Start/End dates from study treatment eCRF	Non-missing dose. Doses of 0 are allowed.
End of treatment date from end of treatment page	No condition.
Tumor (RECIST) assessment date	Evaluation with a response
Date of verification for treatment beyond RECIST 1.1 Progressive disease.	Will the subject continue treatment beyond disease progression as per RECIST 1.1? marked as 'Yes'
PK collection dates	Was sample taken marked as 'Yes'
Vital signs/ECGs/Laboratory date	At least one non-missing parameter value
Performance Status date	Non-missing performance status

Source data	Conditions
Start/End dates of AE	Non-missing verbatim term

The last contact date is defined as the latest complete date from the above list on or before the data cut-off date. The cut-off date will not be used for last contact date, unless the subject was seen or contacted on that date. No date post cut-off date will be used. Completely imputed dates (e.g., the analysis cut-off date programmatically imputed to replace the missing end date of a DAR) will not be used to derive the last contact date. Partial date imputation is allowed for event (death)/censoring is coming from 'Survival information' eCRF.

The last contact date will be used for censoring of subjects in the analysis of OS.

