9.2.2 Follow up

9.2.2.1 Safety follow-up

All subjects receiving study treatment must have safety evaluations for 30 days after the last dose of study treatment. The 30 day safety follow-up can be done by telephone call or visit. Concomitant medications will be collected until the 30-day safety follow-up has been completed or the start of a new antineoplastic therapy, whichever occurs first. A PK and immunogenicity sample should be collected at the 30-day safety follow up visit as described in [Section 8.5.1](#). If the 30-day safety evaluation is conducted by phone, samples do not need to be collected.

Data collected should be added to the Adverse Events CRF, the antineoplastic therapies since discontinuation of study treatment CRF, the Concomitant Medications CRF and the PK/IG CRF. For female subjects of child bearing potential, pregnancy tests will be performed as outlined in [Section 8.4.3](#).

As of 04-Feb-2021, collection of PK and IG samples is terminated. Following approval of protocol amendment 03, antineoplastic therapies since discontinuation of study treatment will not be collected.

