9.2.2.3 Survival follow-up

Following approval of protocol amendment 03, survival follow-up will not be performed. Subjects will enter the survival follow-up period once they complete the safety follow-up and/or disease progression follow-up after treatment discontinuation (whichever is longer). Subjects will then be contacted by telephone every 12 weeks to follow up on their survival status. Any new antineoplastic therapies that have been started since the last contact date will also be collected during these phone calls.

Information on all subsequent therapies received for NSCLC, if any, after study treatment has been completed, will be collected (including start date, stop date, and date of progression if any).

10 Safety monitoring and reporting

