- Date of discontinuation is the date of the end of treatment visit.
- Date of last contact is defined as the last date the patient was known to be alive. This corresponds to the latest date for either the visit date, lab sample date or tumor assessment date. If available, the last known date patient alive from the survival follow-up page is used. If no survival follow-up is available, the date of discontinuation is used as last contact date.
- Date of secondary anti-cancer therapy is defined as the start date of any additional (secondary) antineoplastic therapy or surgery.

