16.1.4.5.3 Incomplete dates for last known date patient alive or death

All dates must be completed with day, month and year. If the day is missing, the 15th of the month will be used for incomplete death dates or dates of last contact.

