2.7.3 Handling of missing values/censoring/discontinuations

Regarding ORR:

- Subjects in the FAS with unknown BOR will be noted as such in the appropriate tables/listings and counted as non-responders in the ORR calculation.
- If there is no baseline tumor assessment, all post-baseline overall lesion responses are expected to be 'Unknown'. If no valid post-baseline tumor assessments are available, the BOR must be "Unknown" unless progression or death is reported.
- If any new anti-neoplastic therapy is taken while on study, any subsequent assessments would be excluded from the BOR derivation.

- Confirmed PR or CR reported prior to any additional anticancer therapy will be considered as responses in the calculation of the ORR irrespective of the number of missed assessments before response.

Regarding DOR:

- If progression or death due to any reasons has not occurred by the date of the cut-off, then the subject will be censored following the same rules defined for PFS in [Section 2.5.3](#).
- If a subject with a CR or PR has no progression or death, the subject is censored at the date of last adequate tumor assessment.

Regarding OS:

- The last date the subject was known to be alive is the last date the subject was contacted or seen by the treating team. If no post-baseline dates are available (before death or a censoring reason occurred), the date of randomization will be used.
- If a subject is not known to have died by the date of the cut-off, OS will be censored at the last date the subject was known to be alive.

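### SAP Table 2-1 dates overall-survival censoring without the 30-day safety contact or concomitant-medication dates, in conflict with SAP 2.7.3 and Protocol 12.5.1

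*SAP*

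**What the plan says.** SAP 2.1.1.6 builds the last contact date from Table 2-1: "The last contact date is defined as the latest complete date from the above list on or before the data cut-off date". It then gives that date its use: "The last contact date will be used for censoring of subjects in the analysis of OS". The table lists survival-page dates, further antineoplastic therapy, study-treatment dates, the EOT date, tumour assessments, verification of treatment beyond progression, PK sampling, vital signs/ECG/laboratory dates, performance status, and "Start/End dates of AE".

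SAP 2.7.3 states a broader rule for the same endpoint: "The last date the subject was known to be alive is the last date the subject was contacted or seen by the treating team". Protocol 12.5.1 censors OS at the last date the subject was known to be alive. Protocol Appendix 16.1.3.2.8 defines last contact through several sources, including visits: "This corresponds to the latest date for either the visit date, lab sample date or tumor assessment date". SAP Section 4 reports no departure from the protocol analysis.

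Amendment 03 ended most of the listed sources. Protocol 9.2.2.3 says: "Following approval of protocol amendment 03, survival follow-up will not be performed". Safety follow-up for 30 days after the last dose stays mandatory (Protocol 9.2.2.1), and its form is flexible: "The 30 day safety follow-up can be done by telephone call or visit". Table 8-2b keeps concomitant medication for the same 30 days, or until a new antineoplastic drug starts if that is sooner.

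**The concern.** OS counts death from any cause with no time window, so a death reported during the 30 days after the last dose is an event. A subject who answers the Day-30 call, and has no AE date late in that window, is censored at EOT or last dose because Table 2-1 cannot use the call. Deaths in the window are kept while some survivors of the same window have already left the risk set. That censoring depends on outcome.

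The SAP also gives two rules that cannot both be programmed when the Day-30 contact is the latest evidence of life. Two programmers could produce different OS curves from the same data. The planned outputs affected are median OS and the OS estimates at 6, 12, 18 and 24 months (SAP 2.7.2).

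**Working it through.** **1. Which Table 2-1 sources survive Amendment 03.**

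- Ended: survival page (Protocol 9.2.2.3); further antineoplastic therapy (9.2.2.1); tumour data (8.3); PK (8.5.1); vital signs, ECG and laboratory results (8.4); performance status (absent from Table 8-2b); treatment beyond progression (6.1.4.1).
- Still active: study-treatment dates, EOT date, AE start/end dates.
- Still required but not listed: 30-day safety contact, concomitant-medication dates.

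**2. Direction relative to actual last contact.** The deaths, and their dates, are the same under both rules. At each death time the risk set under Table 2-1 is contained in the risk set under last-contact censoring. The Kaplan-Meier estimate is a product of factors 1 − d/n. With the same d and an n that is equal or smaller, no factor can be larger. The Table 2-1 curve therefore lies on or below the other, and strictly below once a death occurs while another subject is in the gap.

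**3. Length of the gap.** The contact is about 30 days after the last dose. Censoring at the last dose loses 30 days. If EOT falls 0 to 7 days after the last dose (Appendix 16.1.4.2), the loss is 23 to 30 days. Table 8-1 instead allows EOT up to 7 days after the decision to stop. If that decision comes at the next planned dose, EOT can be 21 + 7 = 28 days after the last dose and the loss is only 30 − 28 = 2 days. An AE date in the window shortens the gap further.

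**4. Subjects exposed.** On 15-Mar-2021, 50 of 76 randomized subjects were still on treatment (Amendment 3 study update): 50/76 = 66%. This is taken as the upper bound.

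**5. The 24-month landmark.** First, the plan's own figure: 35 × 21 / 30.4375 = 24.15 months, which agrees with the stated approximate 24 months. For a subject dosed on schedule from the day of randomization:

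- 35th dose: 34 × 21 + 1 = day 715 (23.5 months)
- EOT within 7 days: day 722 (23.7 months)
- 24 months: 24 × 30.4375 = day 730.5
- 30-day contact: day 745 (24.5 months)

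Allowing 3 days from randomization to first dose and the 4-day dosing window, EOT is at latest day 722 + 3 + 4 = 729, still before the landmark. A contact 7 days early, at day 745 − 7 = 738, is still after it. Without a late AE date, Table 2-1 censors this subject before 24 months and the contact date does not. If EOT is instead dated from a stopping decision at the end of cycle 35 (day 735), the subject stays at risk under both rules.

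**6. Illustrative size.** The documents give no OS assumptions, so the following are assumed.

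(a) Large-sample simulation, N = 400,000. Exponential time to last dose with median 8.5 months, capped at day 715; EOT 0–7 days after last dose; an AE date in the window for 0% or 50% of subjects; 66% or 100% of subjects exposed; the others followed for up to 12 more months. Three mortality patterns were used: constant hazard with median OS 20 months (the figure Protocol 1.1 cites for high PD-L1 expression), and low on-treatment mortality with 3% or 10% dying in the 30 days and a post-treatment median of 10 months.

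| Landmark | Gain in OS from using last contact, all settings | Same, 66% exposed |
|---|---|---|
| 6 months | 0.3 to 1.1 points | 0.3 to 0.6 |
| 12 months | 0.6 to 1.8 points | 0.6 to 1.1 |
| 18 months | 0.7 to 2.3 points | 0.7 to 1.3 |

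Under constant hazard with 66% exposed and no AE dates, 12-month OS moves from 65.0% to 66.1% and median OS from 19.2 to 20.0 months.

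(b) Trial-sized simulation, 1,500 trials per setting, arms of 25 and 51. Accrual over 386 days, survival follow-up ending at day 500, on-study median 9 months, 30-day death risk 5%, 10% or 20%. The difference was 0.2 to 0.7 points at 18 months and 0.3 to 1.1 at 24 months. The assumed accrual is a little longer than the 365 days between 22-Jan-2020, when no subject had been treated, and the halt on 21-Jan-2021.

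**7. Direction against true OS.** In (a) with the 3% pattern, 66% exposed and no AE dates, 12-month OS is 79.9% under Table 2-1, 80.5% with the contact date and 71.2% in truth. Both rules overstate OS because deaths after Day 30 are no longer sought.

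**The case against.** The strongest reply is that the SAP already contains the right rule. SAP 2.7.3 covers a Day-30 call, Protocol 12.5.1 says the same in substance, and derivation detail may sit in the programming specifications, which are not public. This reduces the defect to a conflict between two SAP sections but does not remove it: SAP 2.1.1.6 is the detailed derivation and says outright that its date is used for OS.

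AE start and end dates are listed and are collected through the same 30 days, so a reader who infers that the safety contact is almost the only later evidence of survival goes too far. That part of the reply stands. So does the point that 50 is an upper bound and that not everyone loses a month.

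The effect is also small beside sampling error. Ignoring censoring, a 95% interval near 50% is 1.96 × √(0.25/25) = ±20 points for 25 subjects and 1.96 × √(0.25/51) = ±14 points for 51. No hypothesis is attached to OS, and the rule applies to both arms.

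A reader might also suspect that the EOT date, listed without a condition, could be an administrative date for a lost subject. The documents do not support that. Appendix 16.1.3.2.8 defines the discontinuation date as the EOT visit and makes it the fallback for last contact when survival follow-up is unavailable.

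Finally, neither Protocol 9.2.2.1 nor Table 8-2b shows a field for the date of the Day-30 call. Existing collection is certain only for concomitant medication.

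**Conclusion.** The point holds as a conflict within the plan. Table 2-1, read as written, can censor a subject before a documented alive date, by up to about 30 days, and disagrees with SAP 2.7.3 and Protocol 12.5.1. Relative to censoring at actual last contact, the Kaplan-Meier curve can only be lowered. The size is illustratively about 0.2 to 2 points and rests on assumptions outside the documents. The 24-month effect on 35-cycle completers follows from protocol figures, provided that EOT is dated within about a week of the last dose and no later AE date exists.

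A reader might infer that OS is understated outright. The documents do not support that: with survival follow-up stopped, both rules may overstate true OS, as the example in the working shows. At most 50 of 76 subjects are exposed. OS is secondary and descriptive, so no error rate or power is affected. The correction is worth making because it is cheap and settles which rule applies.

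The day-missing rule in Appendix 16.1.4.5.3 ("If the day is missing, the 15th of the month will be used for incomplete death dates or dates of last contact") is a separate, minor matter. It could place a death before a known alive date, but the documents give no indication of how often that would arise.

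**What to change.** 1. Add to Table 2-1 the concomitant-medication start and end dates, and the 30-day safety follow-up contact date. Where the eCRF has no contact date, use the study-completion or disposition date with status alive, if recorded.
2. Cross-refer SAP 2.1.1.6 and 2.7.3 so that one definition of last date known alive governs OS censoring.
3. Report the number at risk by arm at 6, 12, 18 and 24 months, and state that survival was not followed beyond the safety period after Amendment 03.
4. Optionally, set a day-missing death date no earlier than the day after the last known alive date.

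No condition on the EOT date is needed. The cost is two table rows, a cross-reference and a small derivation change. Concomitant-medication dates are already collected. Whether the contact date needs no new collection depends on the eCRF and should be checked first.

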2.2 Analysis Sets

Full Analysis Set (FAS)

The FAS comprises all subjects to whom study treatment has been assigned by randomization. According to the intent-to-treat principle, subjects will be analyzed according to the treatment they have been assigned to during the randomization procedure. All efficacy endpoints will be analyzed based on the FAS population.

Safety Set

The Safety set includes all subjects who received at least one dose of study treatment (either one in the combination arm). Subjects will be classified according to treatment received, where treatment received is defined as:

- the treatment assigned if it was received at least once, or
- the first treatment received when starting therapy with study treatment if the assigned treatment was never received.

All safety endpoints will be analyzed based on the Safety set.

Pharmacokinetic Analysis Set (PAS) and immunogenicity (IG) set

The **capmatinib pharmacokinetic analysis set (INC-PAS)** includes all subjects who provide at least one blood sample providing measurable capmatinib PK data. For a concentration to be evaluable, subjects are required to:

- receive the planned capmatinib treatments prior to sampling
- for INC280 PK samples taken on or after Cycle 2 Day 1, take the same dose of INC280 for at least 3 consecutive days prior to sampling
- (for pre-dose samples) not to vomit within 4 hours after the last dosing of capmatinib prior to sampling; (for post-dose samples) not to vomit within 4 hours after the dosing of capmatinib
- (for pre-dose sample) have the sample collected before the next dose administration and 9-15 hours after the last dose administration.

The PK parameter analysis for the first 8 patients will include all patients who provide an evaluable PK profile. A profile is considered evaluable if all of the following conditions are satisfied:

- patient receives the planned treatments
- patient provides at least one primary PK parameter
- patient did not vomit within 4 hours after the dosing of INC280
- for Cycle 2 Day 1 profile of INC280, patient took the same dose of INC280 for at least 3 consecutive days prior to sampling
- for Cycle 2 Day 1 profile of INC280, patients are required to have the pre-dose sample collected before the next dose administration and at least 9 hours after the last dose administration of INC280.

The **pembrolizumab pharmacokinetic analysis set (Pembro-PAS)** includes all subjects who provide at least one blood sample providing measurable pembrolizumab PK data. For a concentration to be evaluable, subjects are required to:

- have received one of the planned pembrolizumab treatments prior to sampling
- (for pre-dose samples) have the sample collected before the next dose administration.

The immunogenicity (IG) set includes two parts: IG prevalence set and IG incidence set:

- The IG prevalence set includes all subjects in the FAS with a determinant baseline IG sample or at least one determinant post-baseline IG sample
- The IG incidence set includes all subjects in the IG prevalence set with a determinant baseline IG sample and at least one determinant post-baseline IG sample.

Note: Some subject's data may not be adequate for the reliable estimation of some PK parameters. These cases will be identified and their PK parameters will be excluded from the relevant summaries. The criteria of exclusion will be listed in [Table 2-2](#).

All endpoints related to PK will be analyzed based on the PAS analysis set, unless otherwise specified.

2.2.1 Classification of subjects

Subjects may be excluded from the analysis populations defined above based on the protocol deviations (PDs) entered in the database and/or on specific classification rules defined in [Table 2-2](#).

Table 2-2 Subject classification based on protocol deviations and non-protocol deviation criteria

Analysis set	PDs leading to exclusion	Non-PDs to exclusion
Full analysis set (FAS)	No written inform consent	Subject not receiving a dose of study treatment
Safety set	No written inform consent	Subject not receiving a dose of study treatment
INC-PAS and Pembro-PAS	No written inform consent	Subject not receiving a dose of study treatment.

	C1D1 Pembro PK/IG or INC PK/IG sample not collected or collected after dosing	Subject not providing any evaluable PK concentration for capmatinib or Pembro, respectively
Immunogenicity (IG) prevalence set	No written inform consent	Subject not receiving a dose of study treatment Subjects without a determinant baseline IG sample and at least one determinant post-baseline IG sample
Immunogenicity (IG) incidence set	No written inform consent	Subject not receiving a dose of study treatment Subjects without a determinant baseline IG sample or at least one determinant post-baseline IG sample.

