8.1.1 Information to be collected on screening failures

Subjects who sign an informed consent form and are subsequently found to be ineligible will be considered a screen failure. The reason for screen failure should be entered on the applicable eCRF. The demographic information, informed consent, and Inclusion/Exclusion pages must also be completed for screen failure subjects. No other data will be entered into the clinical database for subjects who are screen failures, unless the subject experienced a serious adverse event (SAE) during the screening phase (see [Section 10.1.3](#) for SAE reporting details). Adverse events that are not SAEs will be followed by the investigator and collected only in the source data. If the subject fails to be randomized, the IRT must be notified within 2 days.

Subjects who are randomized but fail to start treatment, e.g. subjects randomized in error, will be considered as early terminators. The reason for early termination should be recorded on the appropriate eCRF.

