Imaging assessments as described in [Table 8-3](#) should be performed at the time points specified using the same imaging modality used at baseline, irrespective of study treatment interruption or actual dosing (see [Table 8-2](#)). Imaging assessments for response evaluation will be performed every 9 weeks (+/- 7 days) through 45 weeks and every 12 weeks (+/- 7 days) thereafter until disease progression, death, lost to follow-up or withdrawal of consent. Imaging assessments should be scheduled using the randomization date as the reference date (not the date of the previous tumor assessment) and should be respected regardless of whether treatment with study treatment is temporarily withheld or unscheduled assessments performed.

Additional imaging assessments may be performed at any time during the study at the investigator's discretion to support the efficacy evaluations for a subject, as necessary. Clinical suspicion of disease progression at any time requires a physical examination and imaging assessments to be performed promptly rather than waiting for the next scheduled imaging assessment.

Each lesion that is measured at baseline must be measured by the same method (either same imaging method or by photography, including a metric ruler) and when possible, the same local radiologist/physician throughout the study so that the comparison is consistent. If an off-schedule imaging assessment is performed because progression is suspected, subsequent imaging assessments should be performed in accordance with the original imaging schedule.

Combined PET/CT may be used only if the CT is of similar diagnostic quality as a CT performed without PET, including the utilization of IV contrast media. At the discretion of the Investigators, FDG-PET scans may be performed to document progressive disease per RECIST 1.1 ([Section 16.1](#)).

The coded medical images will be used primarily for analysis as described in this protocol; however, the images may also be used for the development and evaluation of new analysis methods directly related to the area of research that this study covers.

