12.1 Analysis sets

12.1.1 Full Analysis Set

The Full Analysis Set (FAS) comprises all subjects to whom study treatment has been assigned by randomization. According to the intent-to-treat (ITT) principle, subjects will be analyzed according to the treatment they have been assigned to during the randomization procedure. All efficacy endpoints will be analyzed based on the FAS population.

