2.5.2 Statistical hypothesis, model, and method of analysis

Due to the study enrolment halt on 21-Jan-2021, the discontinuation of capmatinib in the combination arm and the stopping of efficacy data collection in the eCRF, the initially planned Bayesian PFS analyses for the primary endpoint will become uninterpretable and this study is no longer expected to meet its primary endpoint. As mentioned in Section 12.8 of the current protocol, the Bayesian model will not be performed and the primary endpoint will be summarized instead using KM curves for PFS for each treatment arm. The FAS will be used. Median PFS, with corresponding 95% CI, and 25th and 75th percentiles ([Brookmeyer and Crowley 1982](#), [Klein and Moeschberger 1997](#)) will be presented. KM estimates for PFS proportions at specific timepoints (3, 6, 12, and 18 months), along with 95% CI (Greenwood's formula, [Kalbfleisch and Prentice 2002](#)) will also be provided. The number (%) of events and subjects censored will also be summarized.

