in KEYNOTE-042 (Mok et al 2019). It is therefore reasonable to assume that the median PFS of pembrolizumab is between 7.1 and 10.3 months. We expect around 50% reduction in the HR2 of PFS in capmatinib plus pembrolizumab, after the time-point of risk change in the assumed two-piece exponential distributions.

Table 3-1 presents the operating characteristics of the Bayesian model with different outcome scenarios keeping stable the total sample size (96 subjects) and the number of total PFS events (50) required at the time-point of the primary analysis. With this combination reasonable operating characteristics can be achieved. Description of operating characteristics of alternative sample size can be found in Section 16.3 of the protocol.

Table 3-1 Operating characteristics for scenarios with 96 subjects and 50 events at the primary analysis

Scenarios (capmatinib plus pembrolizumab vs. pembrolizumab) PFS in months (Hazard ratio)	Probability of Success
7.1 vs. 7.1 months (HR2=1)	0.110
8.5 vs. 8.5 months (HR2=1)	0.160
10.3 vs. 10.3 months (HR2=1)	0.196
12.8 vs. 8.5 months (HR2=0.598)	0.716
12 vs. 7.1 months (HR2=0.505)	0.850
15 vs. 8.5 months (HR2=0.496)	0.855
18.5 vs. 10.3 months (HR2=0.501)	0.840

HR2: Hazard ratio after the risk change in the two-piece exponential distributions

4 Change to protocol specified analyses

No change from protocol specified analysis was made.

5 Appendix

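### SAP Table 2-2 drops never-dosed subjects from the Full Analysis Set, contradicting its all-randomised definition; it also ties PK-set membership to a sample drawn before the first infusion

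*SAP*

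**What the plan says.** **FAS.** SAP 2.2 states: "The FAS comprises all subjects to whom study treatment has been assigned by randomization". Protocol 12.1.1 says the same: "The Full Analysis Set (FAS) comprises all subjects to whom study treatment has been assigned by randomization". Both invoke intent-to-treat and place all efficacy endpoints on this set. Neither sets a dosing condition.

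SAP 2.2.1 then says "Subjects may be excluded from the analysis populations defined above", on the basis of recorded protocol deviations or the rules in Table 2-2. In the FAS row, the column for reasons other than deviations reads "Subject not receiving a dose of study treatment". The Safety set row has the same entry. Nothing says when the FAS exclusion applies or does not apply.

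The protocol expects such subjects. Section 8.1.1, having dealt with screen failures, adds: "Subjects who are randomized but fail to start treatment, e.g. subjects randomized in error, will be considered as early terminators". SAP section 4 states: "No change from protocol specified analysis was made".

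**PK sets.** Table 2-2 also lists, as a deviation leading to exclusion, a Cycle 1 Day 1 PK/immunogenicity sample that was missed or was drawn after dosing. The first cell of that row is blank after a page break. Its other entry concerns evaluable PK concentrations, so it reads as a continuation of the INC-PAS/Pembro-PAS row. The set definitions in SAP 2.2 and protocol 12.1.4 contain no Cycle 1 Day 1 condition.

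**The concern.** The FAS cannot both contain every randomised subject and exclude those never dosed. Table 2-2 is the classification rule from which set flags would be programmed, and the SAP does not say whether the text or the table takes precedence.

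Subjects and sites know the assigned arm, so failure to start treatment can depend on it. Removing such subjects then selects on something that happened after randomisation. The endpoints affected are:

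- **ORR.** SAP 2.7.3 keeps subjects with unknown best response in the denominator as non-responders. Dropping never-dosed subjects who have no response can only raise the rate.
- **DCR.** The same applies where unknown best response stays in an intent-to-treat denominator, as protocol 16.1.3.1 allows.
- **PFS.** SAP 2.5.2 promises: "The number (%) of events and subjects censored will also be summarized". Those counts change whenever a never-dosed subject is dropped. The Kaplan-Meier curve changes only if that subject had a counted event or contributed time at risk through scans.
- **OS.** Any effect depends on how much survival information exists for never-dosed subjects. The documents do not establish that, so no size is given.

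For Pembro-PAS, a subject with valid later trough concentrations could be lost because an uninformative pre-treatment sample was missed or drawn late.

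**Working it through.** The plan gives no figure for this point, so there is none to reproduce. The check sets the passages side by side and then illustrates the size.

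**Inputs from the documents.** 76 randomised = 51 combination + 25 control (protocol, Amendment 3 study update). First dose is due within 3 days of randomisation (protocol 6.1.1). A subject with no post-baseline assessment and no counted event is censored at randomisation (SAP 2.5.3). The first scheduled scan is at 9 weeks (protocol Table 8-3).

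**Assumptions.** The number never dosed (k), the responder counts and the early PFS events are not in the documents. The values below are illustrative.

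**ORR.** With x responders among n randomised and k never-dosed non-responders removed, the rate goes from x/n to x/(n − k), a factor of n/(n − k). Intervals are Clopper-Pearson 95%, the SAP's own method.

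| Arm (assumed x) | k = 0 | k = 1 | k = 2 |
|---|---|---|---|
| Control (10) | 10/25 = 40.0% (21.1–61.3) | 10/24 = 41.7% (22.1–63.4) | 10/23 = 43.5% (23.2–65.5) |
| Combination (20) | 20/51 = 39.2% (25.8–53.9) | 20/50 = 40.0% (26.4–54.8) | 20/49 = 40.8% (27.0–55.8) |

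The same k has about twice the effect in the smaller arm: 25/24 = 1.042 against 51/50 = 1.020.

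**PFS at 3 months, control arm.** Assume 24 dosed subjects, 6 with events by month 3 and the other 18 followed beyond it, plus one never-dosed subject.

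| Handling of the never-dosed subject | 3-month Kaplan-Meier | Event proportion |
|---|---|---|
| Dropped | 18/24 = 75.0% | 6/24 = 25.0% |
| Kept, censored at randomisation | 75.0% (never in the risk set at an event) | 6/25 = 24.0% |
| Kept, scanned event-free past month 3 | 19/25 = 76.0% | 6/25 = 24.0% |
| Kept, died at month 1.5 | 18/25 = 72.0% | 7/25 = 28.0% |

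A death at month 1.5 falls before the first scheduled scan, so the rule on two or more missing assessments would not remove it.

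**PK sets.**

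1. Protocol Table 8-9 schedules the Cycle 1 Day 1 pembrolizumab sample immediately before the infusion.
2. SAP 2.2 requires a prior pembrolizumab dose for a concentration to be evaluable, so this sample can never qualify.
3. Pembro-PAS membership needs only one sample with measurable data.
4. The note in SAP 2.2 that points to Table 2-2 concerns leaving PK parameters out of summaries, not membership of the set.
5. Protocol Tables 8-7 and 8-8 schedule capmatinib sampling in Cycles 2, 3 and 4 only, so no Cycle 1 Day 1 capmatinib sample is planned.

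**The case against.** The best reply is that the FAS entry is a copying slip with little consequence. The dosing phrase appears in every row of Table 2-2, the introduction is permissive, and both documents state intent-to-treat. SAP 2.3 and 2.3.1 also base disposition on the FAS and count randomised and treated subjects separately, which has little purpose if everyone in the FAS was treated. That supports the view that all randomised subjects were intended. It does not remove the entry. If the table is programmed literally, the treated percentage becomes 100% by construction and the exclusion is hidden. A discretionary exclusion after randomisation would be no better than a fixed one.

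On size, the objection largely stands. The never-dosed count is unknown and may be zero, the analysis is descriptive, and a shift of 1.7 points is small against a confidence interval about 40 points wide.

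The 76.0% and 72.0% PFS cases are conditional. Protocol 8.3.1 sets scans from randomisation "irrespective of study treatment interruption or actual dosing", but that wording governs timing and does not clearly say that never-treated subjects are scanned. Progression and survival follow-up were written for subjects who stop treatment and ended with Amendment 3. Censoring at randomisation, with an unchanged curve, is the case the documents support most directly.

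On the PK clause, assigning the row depends on reading across a page break. Not collecting an unscheduled capmatinib sample is not a deviation, so the clause should not be read as excluding the whole combination arm. The pembrolizumab problem remains, although collection ended in February 2021 and the number affected is not given.

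**Conclusion.** The concern holds. The FAS row of Table 2-2 contradicts the set's definition in both documents, for a group the protocol foresees, and SAP section 4 declares no change. It should be fixed before database lock.

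The certain effect, if anyone was never dosed, is on the FAS size and on the event and censoring percentages. ORR rises in any arm that has responders and loses never-dosed non-responders, and DCR moves likewise under an intent-to-treat denominator. One such subject raises the control-arm ORR by about 4% in relative terms and the combination-arm ORR by about 2%. A change in the PFS curve requires a counted event or follow-up in a never-dosed subject. All illustrative rates rest on assumed counts, and with no never-dosed subjects the FAS effect is nil.

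The Cycle 1 Day 1 criterion is a secondary point. It holds for Pembro-PAS, on the reading that the row continues the PK-set row.

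**What to change.** In SAP Table 2-2:

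- **FAS row:** delete the dosing exclusion, leaving missing informed consent as the only ground. Keep the dosing criterion for the Safety and PK sets.
- **PK row:** delete the Cycle 1 Day 1 criterion, so that INC-PAS and Pembro-PAS follow the definitions and evaluability conditions in SAP 2.2. Leave the baseline-sample requirement to the immunogenicity incidence set, which already has it. This also disposes of the reference to a capmatinib sample that is not scheduled.

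If the sponsor does intend a randomised-and-treated efficacy set, SAP section 4 must declare and justify it.

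The cost is two deletions in one table, made through a SAP amendment before database lock as SAP section 1 requires. No new data or outputs are needed. Once the FAS again holds all 76 subjects, the disposition table in SAP 2.3.1 will show by arm how many were never treated.
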